11.2 Medical History and Comorbidities

Medical history and comorbidities (past and ongoing) will be presented for the FAS. It will be categorized as follows:

- Past medical history and comorbidities: any disease resolved during the pre-treatment period defined in [Section 9](#) (year prior to cladribine initiation).
- Ongoing comorbidities: any disease that started or is ongoing at cladribine initiation

Any disease that was resolved more than one year prior to cladribine initiation is not relevant will not be included in the analysis.

Medical history and comorbidities will be summarised from the “Medical History and comorbidities” eCRF page, using the most recent Medical Dictionary for Regulatory Activities (MedDRA) version at the time of database lock, preferred term (PT) as event category and system

organ class (SOC) body term as body system category. Each participant will be counted only once within each PT or SOC.

12 Previous or Concomitant Therapies/Procedures

Medications will be presented for the FAS by the most recent prior DMT and overall. Previous and concomitant medications will be presented in separate tables and are defined as follows:

- Previous medications are defined as any medication discontinued during the year prior to cladribine initiation.
- Concomitant medications are defined as any medication taken during the course of the study, with a starting date greater than or equal to the administration of cladribine , or with a starting date prior to the administration of cladribine and ongoing at the time of the administration of cladribine .

The World Health Organization Drug dictionary (WHO-DD) will be used for coding of prior and concomitant medications and they will be described using PT as applicable. The most recent version of WHO-DD available at the time of data-cut will be used for medications coding.

Previous and concomitant medications will be listed. Concomitant procedures, if any, will also be listed.

13 Exposure

The following analyses will be performed based on the FAS by the most recent prior DMT and overall.

All calculations and summaries for treatment in Year 1 and Year 2 of cladribine will be based on “Treatment with cladribine Tablets” eCRF page. For additional courses of cladribine (Year 3, Year 4, Year 5 data will be pulled from the “Prior and Subsequent Disease Modifying Therapy” eCRF page if the treatment reported is “cladribine”.

The summary of cladribine exposure will include the following information:

- Number of tablets taken per week of ‘Year 1’, ‘Year 2’ and each subsequent course of cladribine
- Total number of tablets taken on ‘Year 1’, ‘Year 2’ and each subsequent course of cladribine
- Cumulative number of tablets taken (cumulative over Year 1 and Year 2, and cumulative over all courses of cladribine treatment)
- Number % of patients with no dose and dose delayed (with the corresponding reasons)
- Number % of patients with a complete course of cladribine at ‘Year 1’, ‘Year 2’, any additional courses of cladribine treatment and overall

14 Effectiveness

The following analyses will be performed based on the FAS by the most recent prior DMT and overall.

14.1 *Primary Outcome: ARR*

14.1.1 *Primary Objective: Derivation and analysis of the primary outcome: ARR*

The annualised relapse rate (ARR) will be derived from the 'Clinical Confirmed Relapses' CRF page.

The relapses observed will be assigned for the calculation for the ARR as indicated on [Table 1](#) in Section 9.6.

The ARR for a patient will be calculated by dividing the number of clinicians confirmed relapses observed within each period (Year) by the person-years of the patient in the period.

The person-years for a patient will be assigned as follows:

- $(365.25-84)/365.25$ years for time-point 'Year 1' for the full effectiveness period (main analysis)
- $(365.25-56)/365.25$ years for time-point 'Year 1' for the amplified effectiveness period (sensitivity analysis #1)
- 1 year for time-point 'Year 1' for the full treatment effectiveness period (sensitivity analysis #2)

And 1 year for each other interval (-1, 2, 3, 4, 5) unless the date of last contact occurs within that interval. In this case that interval person-years will be calculated until the date of last contact. The patient will not contribute to the ARR calculation for the following intervals (if any).

The 95% confidence interval (CI) will be calculated using the exact Poisson method.

14.2 *Secondary Outcomes*

14.2.1 *Secondary Objective: Derivation and analysis of the secondary outcome: RFR*

The relapse-free rate (RFR) is defined as the time from the on-treatment period start date (see [Table 3](#)) until the date of the first relapse or death as assessed by the investigator:

- RFR (years): $(\text{First relapse date or death or date of censoring} - \text{on-treatment start date} + 1) / 365.25$.

The main analysis will be based upon the full effectiveness period start date. Sensitivity analyses will be repeated on the amplified and full treatment periods start dates respectively.

Patients who did not have any relapse or have died will be censored at the date of last contact.

The RFR will be summarised using the total number and % of patients with an event and the type of event (relapse, death). The number and % of censored patients will be also presented.

The RFR and associated 95% CI will be summarised at yearly intervals using the Kaplan-Meier (KM) method, the median RFR and corresponding 95% CI (whenever estimable) will be also included. KM curves will be provided.

14.2.2 *Secondary Objective: Derivation and analysis of the secondary outcome: Treatment discontinuation*

A patient will be considered to have discontinued the treatment if he/she does not complete the full treatment course (i.e. 2 weeks in 2 consecutive years). In this case, date of treatment discontinuation will be the date of switch to other DMTs, i.e. the earliest start date of any DMTs following the last date of administration of cladribine. If the patient did not receive any DMTs after the last dose of cladribine, the date of treatment discontinuation will be the last date of administration as recorded in the 'Treatment with Cladribine Tablets' CRF page.

The number and % of patients who discontinued the treatment will be summarised in the disposition table. The number and % of patients who switched to other DMTs will also be reported.

The reason for treatment discontinuation will be derived from the record where the last date of administration is recorded. Reasons will be summarised as follows:

- AE (as per CRF)
- Missed dose (as per CRF)
- Other (as per CRF)

Patients who did not complete the treatment and did not have any of the above reasons reported to their last record will be classified as:

- 'Incomplete course of cladribine treatment'

14.2.3 *Secondary Objective: Derivation and analysis of the secondary outcome: Subsequent DMTs*

DMTs are treatments reported in the "Prior and Subsequent Disease Modifying Therapy" eCRF page excluding cladribine. The number and % of patients with subsequent DMTs will be summarised by preferred names.

The time to first subsequent DMT (T1DMT) is defined as the time from the date of last dose of cladribine until the date of the first subsequent DMT:

- T1DMT (years): (Date of start of first subsequent DMT - last cladribine administration date + 1)/365.25.

Patients who did not start any subsequent DMT will be censored at the date of last contact.

The T1DMT will be summarised using the total number and % of patients with an event. The number and % of censored patients will be also presented.

The T1DMT and associated 95% CI will be summarised at yearly intervals using the KM method, the median TSDMT and corresponding 95% CI (whenever estimable) will be also included. KM curves will be provided.

Time to second subsequent DMT (T2DMT) will be derived as follows:

- T2DMT (years): (Date of start of second subsequent DMT - last cladribine administration date + 1)/365.25.

The T2DMT will be summarised in the same way of T1DMT only if at least 5% of patients have a second subsequent DMT recorded.

14.2.4 *Secondary Objective: Derivation and analysis of the secondary outcome: EDSS and disability progression*

The Annual EDSS results at cladribine initiation and at Year 2 and the corresponding change from baseline (i.e. cladribine initiation) will be summarised using descriptive statistics. Scores will be derived from the 'Annual EDSS scores' CRF page. All other assessment will be presented in a listing.

The number and % of patients with disability progression confirmed over 6 months at Year 2 after cladribine initiation will be also summarised.

EDSS progression is defined as an increase in the EDSS scale as follows:

- If the EDSS score at cladribine tablet initiation is 0, the increase must be ≥ 1.5 units
- If the EDSS score at cladribine tablet initiation is ≥ 0.5 or ≤ 4.5 , the increase must be ≥ 1.0 units
- If the EDSS score at cladribine tablet initiation is ≥ 5.0 , the increase must be ≥ 0.5 units.

EDSS assessments will be assigned to time windows as defined in Section 9.6.

15 Safety Analyses

Safety analyses will be performed based on the FAS by the most recent prior DMT and overall.

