9.6 Time Window

For analyses conducted at yearly intervals (e.g. relapse rate at each year) the date of the event will be assigned an analysis time-point according to [Table 1](#):

Table 1. Time windows for relapses analysis

Time-point	Study day	
	From	To
Year -1	-365	-1
Year 1	84*	365
Year 2	366	731
Year 3	732	1096
Year 4	1097	1461
Year 5	1462	1826

*Relapses occurred within the induction period window of 12 weeks (84 days) will not be included in the main analysis. Sensitivity analyses will be repeated changing Year 1 interval to (56 to 365 days) and (1 to 365 days) respectively.

For EDSS analysis on disability progression the [Table 2](#) will be followed:

Table 2. Time window for EDSS analysis

Time-point	First assessment		
	Study day		
	From	Mid-point	To
Baseline	-60	-	1
Year 2 (treatment start date) OR Year 2	183	365	548

The closer assessment to the Year 2 treatment start date will be used. If the patient does not receive any treatment at Year 2, [Table 2](#) time-window will be used to derive the Year 2 EDSS assessment. The confirmatory EDSS score assessment (used to confirm disability progression) will be selected in the (+91; +272) days interval from the 'Year 2' assessment date. In case of multiple assessments within this window the closer to +182 days from the 'Year 2' assessment date will be picked.

In case of multiple assessments at the same distance of the mid-point the earliest one will be considered for the analysis. All measurements will be listed.

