9.7 Definition of On-treatment Period

Three different on-treatment periods will be defined based upon the induction period definition as follows:

Table 3. On-treatment periods

On-treatment period	Study day	
	From	To
Full effectiveness	84	Minimum of - Cut-off date - Date of death
Amplified effectiveness	56	
Full treatment	1	

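### The main relapse-free and time-to-first-relapse analysis starts at Day 84, not at cladribine initiation as the protocol and SAP section 5 state, and SAP section 7 does not declare the change

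*SAP*

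**What the plan says.** **Protocol.** Sections 8.2 (objectives), 9.1.2.2 (outcomes) and 9.7.3 (Secondary Outcome Analysis) all place the origin for time to first relapse, and for the yearly relapse-free proportions, at cladribine initiation. Section 9.7.3 (Primary Outcome Analysis) allows an induction period as an option, and only for the Year 1 annualised relapse rate (ARR).

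**SAP section 5** repeats the initiation origin for both endpoints and refers both to section 14.2.1. **SAP section 7** reports no departure from the protocol's analyses.

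**SAP 14.2.1** defines the relapse-free outcome (RFR) differently. It is "defined as the time from the on-treatment period start date", with a pointer to Table 3 in section 9.7. Table 3 gives three start days: 84 (full effectiveness), 56 (amplified effectiveness) and 1 (full treatment). "The main analysis will be based upon the full effectiveness period start date", which is Day 84. The Day 56 and Day 1 starts are sensitivity analyses.

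Three further statements bear on how the analysis would be run:
- Censoring (14.2.1): "Patients who did not have any relapse or have died will be censored at the date of last contact".
- Yearly estimates (14.2.1): "The RFR and associated 95% CI will be summarised at yearly intervals using the Kaplan-Meier (KM) method".
- Induction window (footnote to Table 1, section 9.6): "Relapses occurred within the induction period window of 12 weeks (84 days) will not be included in the main analysis".

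**The concern.** Time from Day 84 to first relapse is a different quantity from time since initiation. A reader who relies on sections 5 and 7 would take the main result for the protocol's endpoint. In a descriptive study the estimate is the product, so its label has to be right.

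The moved origin also leaves two gaps in 14.2.1:

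1. **Relapses before Day 84.** The section's formula gives them a zero or negative time. The Table 1 footnote, together with use of the full analysis set, points to keeping these patients at risk as relapse-free. But 14.2.1 does not cite the footnote, and its censoring sentence covers only patients without any relapse. An early relapser with no later relapse fits neither description.
2. **The meaning of a year.** The 14.2.1 clock starts at Day 84. Section 5 asks for years after initiation, and section 9.6 assigns Table 1 windows to "For analyses conducted at yearly intervals (e.g. relapse rate at each year" and similar analyses.

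How far the main figure lies from the initiation-based one, and in which direction, depends on how these gaps are resolved.

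**Working it through.** **Inputs.** Start days 84, 56 and 1: SAP Table 3. Year ends on Days 365, 731, 1096, 1461 and 1826: SAP Table 1. Planning rate 0.14 per year and sample sizes 90 and 200: protocol 9.5. The documents give no relapse rate for the first 12 weeks, so early rates r of 0, 0.14, 0.3 and 0.5 per year are assumed.

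**The plan's own figure.** Protocol 9.5 gives a 95% half-width of 0.072 for 0.14 with 90 patients. It reproduces as 1.96 × √(0.14 × 0.86 / 90) = 0.0717. The present point does not depend on it.

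**Step 1: the 14.2.1 formula before Day 84.** Time = (event day − 84 + 1) / 365.25.
- Day 83: (83 − 84 + 1) / 365.25 = 0.
- Day 40: (40 − 84 + 1) / 365.25 = −0.118 years.

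**Step 2: where the years fall.** On the 14.2.1 scale, year y is Day 84 + 365.25y − 1, or about Days 448, 814, 1179, 1544 and 1909. Each is 83 days after the corresponding Table 1 year end.

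**Step 3: size.** Assume a constant rate of 0.14 per year after Day 83, rate r over the first 83 days, and early relapsers kept at risk.
- From initiation: S(y) = exp[−r × 83/365.25 − 0.14 × (365.25y − 83)/365.25].
- Main analysis, 14.2.1 scale: A(y) = exp(−0.14y). A(1) = 86.9%, A(4) = 57.1%.
- Main analysis, Table 1 days: B(y) = exp[−0.14 × (365.25y − 83)/365.25]. B(1) = 89.7%, B(4) = 59.0%.

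Differences are in percentage points.

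| Early rate r | S(1) | A − S, 1 yr | B − S, 1 yr | S(4) | A − S, 4 yr | B − S, 4 yr |
|---|---|---|---|---|---|---|
| 0 | 89.7% | −2.8 | 0 | 59.0% | −1.8 | 0 |
| 0.14 | 86.9% | 0 | +2.8 | 57.1% | 0 | +1.8 |
| 0.3 | 83.8% | +3.1 | +5.9 | 55.1% | +2.0 | +3.9 |
| 0.5 | 80.1% | +6.8 | +9.6 | 52.6% | +4.5 | +6.3 |

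**Step 4: direction.** With early relapsers kept at risk, B cannot fall below S whatever the rates, because being relapse-free from Day 84 to t is a weaker condition than being relapse-free from Day 1 to t. A has no fixed direction: it exceeds S when the early rate is above the later one and falls short when it is below.

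**Step 5: patients with an uncounted relapse in Days 1–83.** Probability 1 − exp(−r × 83/365.25):
- r = 0.14: 3.1%, about 3 of 90 or 6 of 200.
- r = 0.3: 6.6%, about 6 or 13.
- r = 0.5: 10.7%, about 10 or 21.

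**The case against.** The strongest reply is that little is hidden or lost. SAP 14.2.1 states its start day openly, the initiation-based analysis is planned, and the study tests no hypothesis, so no error rate is affected. The SAP's modification history lists no change of origin after version 1.0, so nothing suggests a data-driven choice. Sharing an induction period with the main Year 1 ARR is a coherent design. All of this stands. It limits the seriousness, but it does not make section 5 or section 7 correct, and the protocol's induction clause does not extend to this outcome.

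On early relapses, the natural reading is that first relapse means first within the period, as the footnote implies. That is probably the intention, but 14.2.1 does not say so and its censoring sentence does not fit it.

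On the time scale, the formula itself suggests years from Day 84, and the Table 1 reading produces the largest differences. That is fair, and those differences should be read as one of two possible readings. The ambiguity nevertheless has a textual basis in section 5 and in the rule in section 9.6.

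Finally, at 0.14 per year throughout, the difference on the 14.2.1 scale is exactly zero, and the other early rates are assumptions. This is correct: the size and sign are unknown, and no distortion has been demonstrated.

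**Conclusion.** The concern holds. The main analysis of relapse-free status and time to first relapse uses a different origin from the endpoint in the protocol and in SAP section 5, and section 7 does not declare it. The handling of early relapses and the yearly time scale also need to be written down.

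Over assumed early rates of 0 to 0.5 per year, the one-year figure moves by -2.8 to +6.8 points (14.2.1 scale) or 0 to +9.6 points (Table 1 days). At four years the ranges are -1.8 to +4.5 and 0 to +6.3 points. They rest on a constant 0.14 per year after Day 83 and on keeping early relapsers at risk. The mismatch in the text depends on none of these assumptions. It should be corrected, but the initiation-based result will be produced in any case.

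**What to change.** **Preferred.** Make the planned Day 1 (full treatment period) analysis the main one for time to first relapse and the yearly relapse-free proportions, with Day 56 and Day 84 as sensitivity analyses. For those two, state in 14.2.1 that patients with an earlier relapse stay at risk (or give another explicit rule), report how many there are, and label the time axis and yearly estimates as years after the start day.

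**Alternative.** If Day 84 stays as the main analysis, declare it in section 7, align section 5, and add the same rule, count and labels.

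**Cost.** SAP wording only, since all three analyses are already planned. Under the preferred option the main RFR and the main Year 1 ARR would start on different days, so the planned Day 1 ARR should be shown beside the RFR. The headline relapse-free figure could move either way relative to the 14.2.1 scale. Relative to a curve read on the Table 1 days with early relapsers at risk, it could only stay the same or fall.

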15.1 Adverse Events

The Treatment-Emergent Adverse Event (TEAE) are those events with onset dates occurring within the full treatment period as defined in Section 9.7.

The AEs related to study treatment are those events with relationship missing or “Related”.

All analyses described in this section will be based on TEAEs if not otherwise specified. The AE listings will include all AEs (whether treatment-emergent or not). AEs outside the on-treatment period will be flagged in the listings.

Unless otherwise specified, TEAEs will be summarised by number and percentage of patients with the TEAE in the category of interest, primary SOC and PT in decreasing frequency.

Each participant will be counted only once within each SOC or PT. If a participant experiences more than one AE within a SOC or PT for the same summary period, only the AE with the strongest relationship or the worst severity, as appropriate, will be included in the summaries of relationship and severity.

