- Selected adverse events: Reporting of AEs once informed consent has been obtained (as described in [Section 11](#)), with special focus on:
  - grade 3 lymphopenia
  - grade 4 lymphopenia
  - herpes infections
  - serious infections (infections for which a hospitalisation is initiated or extended), opportunistic infections (new onset or reactivation of latent infection)
  - malignancies.

For each AE, the start date, end date, classification of serious or non-serious, and outcome should be reported.

Derived and transformed data needed for the analysis are described in [Section 9.7.2](#).

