#### Secondary Outcome Analysis

The proportion of patients who remain relapse-free in each year after treatment initiation (among patients active at start of each year), at 4 years after treatment initiation and at 5 years after treatment initiation (among patients with 5 years observation time available), and the time from cladribine tablet initiation to first relapse will be described using Kaplan-Meier method. Kaplan-Meier survival curve will be plotted (overall and by most recent prior DMT subgroup) and a table with the probabilities of remaining relapse-free in each year after initiation of treatment will be produced.

The proportion of patients who discontinued cladribine tablets and reasons for discontinuation will be summarised using descriptive statistics.

Subsequent DMTs (none or by DMT type) received after treatment with cladribine tablets will be described up to 5 years after cladribine tablet initiation. The proportion of patients who did not receive any other DMT up to a total of 4 years and up to a total of 5 years (among patients with 5 years observation time available) after cladribine tablet treatment initiation will be analysed using descriptive statistics. Depending on the availability of data and the missing data pattern, a survival analysis may be performed to account for loss to follow-up patterns.

The annual EDSS scores at treatment initiation and start of cladribine tablet treatment at Year 2 will be summarised using descriptive statistics. The proportion of patients with disability progression confirmed over 6 months at 2 years after cladribine tablet initiation will be summarised using descriptive statistics.

The number and percentages of patients with AEs will be reported, and the number of AEs itself. The incidence rates of AEs will be summarised by system organ class and preferred term using the Medical Dictionary for Regulatory Activities (MedDRA). Additional summaries will be presented by severity. The AEs will be reported overall, and as stratified in the last prior MS DMT subgroups (as defined in [Table 2](#)).

CCI

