## 11 Adverse Events

### 11.1 Definitions

An AE is any untoward medical occurrence in a patient or clinical study subject administered a pharmaceutical product and which does not necessarily have a causal relationship with this treatment. An AE can therefore be any unfavourable and unintended sign (including an abnormal laboratory finding), symptom, or disease temporally associated with the use of a medicinal product, whether or not considered related to the medicinal product.

Investigators should assess the severity/intensity of any AE as follows:

**Mild:** The subject is aware of the event or symptom, but the event or symptom is easily tolerated.

**Moderate:** The subject experiences sufficient discomfort to interfere with or reduce his or her usual level of activity.

**Severe:** Significant impairment of functioning: the subject is unable to carry out usual activities.

A serious adverse event is any AE as defined above, which also fulfils at least one of the seriousness criteria below:

- Results in death
- Is life-threatening
- Requires in-patient hospitalisation or prolongation of existing hospitalisation
- Results in persistent or significant disability/incapacity
- Is a congenital anomaly/birth defect
- Is otherwise considered as medically important

 Life-threatening in this context refers to a reaction in which the patient was at risk of death at the time of the reaction; it does not refer to a reaction that hypothetically might have caused death if more severe.

 Medical and scientific judgement should be exercised in deciding whether other situations should be considered as serious reactions, such as important medical events that might not be immediately life-threatening or result in death or hospitalisation but might jeopardise the patient or might require an intervention to prevent one of the other outcomes listed above. Such important medical events should be considered as serious.

Examples of such events are intensive treatment in an emergency room or at home for allergic bronchospasm, blood dyscrasias or convulsions that do not result in hospitalisation or development of dependency or abuse. As a guidance, the important medical event terms list is intended to be used for assessment of suspected adverse reactions (see EMA/207865/2017).

---

Any suspected transmission via a medicinal product of an infectious agent is also considered a serious adverse reaction.

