## **11.2 Management and Reporting of Adverse Events**

In this study, safety data collection is based on secondary use of pseudo-anonymised data from existing patient records. Any AEs will be abstracted from the patient records, regardless of seriousness or relationship to cladribine tablets, from the date of initiation of treatment with cladribine tablets until the end of the study period.

Reports of the selected AEs (as listed in [Section 9.1.2.2](#)) will be summarised in the final study report(s).

The investigator will comply with UK pharmacovigilance requirements as defined by HMR (Part-11) to spontaneously report appropriate safety data to the Medicines and Healthcare products Regulatory Agency (MHRA) (e.g., Yellow Card Scheme) as applicable or directly to Merck Serono Ltd.

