15.1.1 All Adverse Events

The AEs will be summarised using the latest version of MedDRA PT as event category and MedDRA primary SOC body term as body system category.

Incomplete AE-related dates will be handled as specified in Section 9.10.

The following tables will be created:

- TEAE summary table with the number and percentage of patients that have:
 - TEAE
 - TEAE of Special Interest (TEAESI)
 - Grade 3 Lymphopenia
 - Grade 4 Lymphopenia
 - Herpes infections
 - Serious/opportunistic infections
 - Malignancies
 - TEAE leading to death

- TEAE leading to cladribine dose reduction
- TEAE leading to cladribine dose increase
- TEAE leading to cladribine temporary interruption
- TEAE leading to cladribine permanent discontinuation
- TEAE not recovered/resolved
- Any serious TEAE:
 - TEAESI
 - Leading to death
 - Leading to cladribine dose reduction
 - Leading to cladribine dose increase
 - Leading to cladribine temporary interruption
 - Leading to cladribine permanent discontinuation
 - Not recovered/resolved
- Cladribine-related TEAE:
 - TEAESI
 - Serious
 - Leading to death
 - Leading to cladribine dose reduction
 - Leading to cladribine dose increase
 - Leading to cladribine temporary interruption
 - Leading to cladribine permanent discontinuation
 - Not recovered/resolved
- The number and percentages of patients with TEAE by Primary SOC and PT
- The number and percentages of patients with TEAESI by Primary SOC and PT
- The number and percentages of patients with serious TEAE by Primary SOC and PT
- The number and percentages of patients with TEAE related to cladribine by Primary SOC and PT

TEAESI will be individuated using standardized and/or customized MedDRA queries that will be shared by Merck safety department using the dictionary version available at the time of the final analysis data-cut.

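### Counting adverse events with missing relationship as cladribine-related may inflate the related-event tables, because the protocol does not name causality among the items collected

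*SAP*

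**What the plan says.** SAP 15.1 defines relatedness in one sentence: "The AEs related to study treatment are those events with relationship missing or" given as related. It then reduces multiple events per participant, so that "only the AE with the strongest relationship or the worst severity, as appropriate, will be included in the summaries of relationship and severity".

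SAP 15.1.1 builds two outputs on that definition. One is a cladribine-related block in the TEAE summary table, with rows for serious events, events leading to death and events leading to permanent discontinuation, among others. The other is a table of "The number and percentages of patients with TEAE related to cladribine by Primary SOC and PT".

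The protocol describes collection differently. Section 9.3 states: "For each AE, the start date, end date, classification of serious or non-serious, and outcome should be reported". Section 11.1 adds one investigator judgement: "Investigators should assess the severity/intensity of any AE as follows". Section 11.2 says that "safety data collection is based on secondary use of pseudo-anonymised data from existing patient records", and that events are abstracted "regardless of seriousness or relationship to cladribine tablets". Apart from counts, incidence rates by SOC and PT, and prior-DMT subgroups, the AE analysis in protocol 9.7.3 says: "Additional summaries will be presented by severity". It plans no summary by relationship.

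**The concern.** Treating a missing relationship as related is a sensible worst case when an investigator judges nearly every event as it happens and blanks are rare. This study differs. Treatment began at least 3 years before enrolment, events are taken from routine charts, and the protocol text does not tell anyone to judge causality. Protocol 9.9 itself warns that data may be missing.

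In that setting a blank may only mean that no one wrote down an opinion. The rule turns the blank into a drug-related event, and the summary tables do not show how many counted events were blanks. A reader could take gaps in charting for evidence on causality, including in the serious and fatal rows. Safety is also tabulated by most recent prior DMT, so uneven charting could produce apparent differences between subgroups.

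**Working it through.** The plan states no figure for related events, so there is nothing to reproduce. The check sets the texts side by side and then shows how the rule behaves.

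**Step 1: is causality among the named items?**

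| Item | Protocol, data collection | SAP, use in AE tables |
|---|---|---|
| Start and end dates | 9.3 | 15.1, treatment-emergent definition |
| Seriousness | 9.3 | 15.1.1 |
| Outcome | 9.3 | 15.1.1, not recovered/resolved |
| Severity | 11.1, not in the 9.3 list | 15.1, worst severity |
| Action taken with cladribine | not named in the 9.3 list | 15.1.1, dose change, interruption, discontinuation |
| Relationship | only in 11.2, to say that events are collected whatever it is | 15.1 and 15.1.1 |

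The mention in 11.2 sets the scope of collection; it is not a data item. Severity and action taken show that the 9.3 list is not exhaustive, so absence from it does not prove that relationship is not collected.

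**Step 2: what is the SAP's default for missing categories?** SAP section 9 (Tables and Descriptive Statistics) keeps missing observations of a qualitative variable in the denominator and shows them as their own category. SAP 9.10 evaluates data as observed, with exceptions allowed where specified. The 15.1 rule is such an exception, and no reason is given for it.

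**Step 3: how far could the rule move the result?** Let m be the share of events with missing relationship and p the share recorded as related among those assessed. The documents give neither, so both are assumptions. The share of events classed as related is

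m + (1 − m) × p.

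| m | p = 0.10 | p = 0.30 |
|---|---|---|
| 0 | 10% | 30% |
| 0.25 | 0.25 + 0.75 × 0.10 = 32.5% | 47.5% |
| 0.50 | 0.50 + 0.50 × 0.10 = 55% | 65% |
| 0.75 | 0.75 + 0.25 × 0.10 = 77.5% | 82.5% |
| 1 | 100% | 100% |

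**Step 4: events versus patients.** The SAP tables count patients, and one blank is enough to make a patient related. Suppose a patient has k = 3 independent events and p = 0.10. The probability of at least one event classed as related is 1 − (1 − s)³, where s is the event-level share from step 3:

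- m = 0: 1 − 0.90³ = 27.1%
- m = 0.25: 1 − 0.675³ = 69.2%
- m = 0.50: 1 − 0.45³ = 90.9%
- m = 1: 100%

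Blanks probably cluster by site or patient, so independence is a simplification. These figures illustrate the mechanism and are not a forecast.

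**The case against.** The strongest reply is that a relationship field probably exists and may be well completed. The SAP names a coded value for related events and has a rule for the strongest relationship. Protocol 3.1 makes the investigator responsible for recording adverse reactions, and protocol 9.4 provides for querying missing data. If the field is complete, the rule has no effect. This stands, and it rules out two stronger readings. A reader might infer that relationship is not collected at all, or that the related tables will simply repeat the all-TEAE tables. The documents support neither: the 9.3 list is incomplete, and full duplication is only the limiting case m = 1.

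It is also true that missing-as-related is a usual conservative convention, openly prespecified. A reader might infer that it breaches the no-imputation rule. It does not, because SAP 9.10 allows stated exceptions and protocol 9.7.2 excludes imputation only in general.

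Third, the stakes are limited. The protocol's safety outcome is the rate of selected events, not related events, in a descriptive study without a comparator. Fatal related events can be few: patients had to be alive to consent at least 3 years after initiation, so deaths can enter only after enrolment, with the second chart review about one year later. The listings show all events and flag imputed information, and the all-TEAE tables stand alongside.

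What remains is that listings do not correct a summary table. Nothing in the planned tables tells the reader how much of a related count is unrecorded causality.

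**Conclusion.** The concern holds as a foreseeable and avoidable risk of inflation. It is not a demonstrated error of known size. The SAP counts missing relationship as related, the protocol does not name causality among its AE items, and the data come from existing charts. If missingness is substantial, the cladribine-related tables will be inflated by unrecorded causality. The effect runs from none (complete field) to full equality with the all-TEAE tables (nothing recorded).

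Where this study falls in that range cannot be derived from the documents. The percentages above rest on assumed values of p, m and k. Comparing them with the m = 0 row also assumes that unrecorded events are related as often as recorded ones, and no data can support that when nothing is recorded. The primary and secondary outcomes as the protocol defines them are untouched.

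**What to change.** Check the eCRF first and state in SAP 15.1 whether relationship is recorded and by whom.

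- **If it is recorded:** in the relationship summaries, show related, not related and not recorded as separate categories, in line with the default in SAP section 9. Base the cladribine-related count on recorded causality, and keep related or not recorded as a line labelled worst case. For patients with several events in a SOC or PT, rank them related, then not recorded, then not related. The first two categories then add up to the worst-case line.
- **If it is not recorded:** drop the cladribine-related block and the related-TEAE table, because they would only repeat the all-TEAE results.

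The cost is one SAP sentence and one extra column. The recorded-related count will be less conservative than the present rule, but the worst-case line keeps that figure, so no safety information is lost. If the field proves complete, no number changes.
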